## General principles

The analysis and reporting of the results will follow the CONSORT guidelines. [1] Baseline characteristics will be tabulated by Dexamethasone and placebo groups using appropriate summary statistics and will include PSQI score. [2] Data for the primary endpoint will be derived from those patients enrolled into the PADDI-SLEEP substudy (those who completed the extra sleep questionnaires). Data for all endpoints will be analysed using the modified intention-to-treat (mITT) and per protocol (PP) populations, with the mITT analysis regarded as the principal analysis. Full definitions of mITT and PP are provided below.

Further sensitivity analyses will make post-hoc adjustment for any variables exhibiting substantial imbalance across treatment arms at baseline (Table 1). Interpretation of all endpoints will be based on post estimates, confidence intervals and P-values. A nominal 5% significance level will be employed.

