### B. Per Protocol (PP) population

[figure not shown]
The PP population will comprise those patients who completed the treatment to which they were originally allocated, meaning ONLY those patients who receive a single dose of study drug or placebo according to their original randomised allocation. This analysis specifically excludes patients who were not given their randomised study drug at the commencement of surgery **AND** patients who received their study drug but also receive non-study glucocorticoid within the 24 hours following surgery. This also excludes patients randomised to dexamethasone whose randomisation was overridden and received open-label dexamethasone within the 24 hours following surgery. Patients who withdraw consent will have their data used up until the time of withdrawal.

The primary analyses will be in the mITT population, per protocol (PP) populations and a sensitivity analyses will make post-hoc adjustment for any variables exhibiting substantial imbalance across treatment arms at baseline. The mITT analysis will be undertaken as per the main Statistical Analysis Plan for the PADDI trial. The per protocol analysis will only exclude those who did not get the study drug or those who got non-study dexamethasone during surgery or in PACU, that is they received non-study dexamethasone prior to the primary outcome occurrence. Because the patients not meeting the PP population definition have been excluded, there may no longer be balance in patient characteristics between dexamethasone and placebo arms. The baseline and pre-operative characteristics in the dexamethasone and

placebo arms will be tabulated and compared for the 'compliant' (PP) patients. Any variables exhibiting imbalance will be adjusted for.

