## Outcomes

The primary outcome is sleep quality on night one (as assessed using the RCSQ). As the distribution of the sleep score is not normal, median regression will be undertaken to assess the difference in medians between the two treatment groups. For the sensitivity analysis, baseline characteristics will be examined and adjustment will be made for differences between the groups. The variable, preop sleep quality, is considered a major confounder and will be included in the adjusted models.

Histogram of sleep quality night one showing two peaks.

The secondary outcome is sleep quality on night two. The same analysis will be undertaken as per night one. Some people would have been discharged on day 1 but for consistency the same variables will be adjusted for as for night one in the sensitivity analysis.

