## Postoperative variables of interest

1. Any nausea or vomiting postoperatively to 24 hours following surgical incision.
2. Any antiemetic usage postoperatively to 24 hours following surgical incision.
3. Nausea –
  - a. Worst nausea as measured on a numerical rating scale (numerical rating scale [NRS], 0–10) in PACU and post PACU up to the first 24 hours following surgical incision.

- b. Antiemetic usage in each of these periods.
4. Vomiting- Any vomiting and number of vomiting events in PACU and post PACU up to the first 24 hours following surgical incision.
  5. Highest pain score (NRS, 0–10) at rest and on movement in PACU and post PACU up to the first 24 hours following surgical incision.
  6. Quality of recovery score Day
  7. Sleep location night 1 and night 2
  8. Noise level night 1 and night 2
  9. Non-study dexamethasone intraoperative, PACU and day 1

These outcomes will be tabulated according to the treatment group but no formal comparison will be performed because we know that dexamethasone administration alters these outcome variables. It is also possible that these outcomes might interact with the sleep outcomes, but we do not plan to examine this. For non-normal continuous distributions, median regression via quantile regression will be undertaken. For binary outcomes, binomial regression to estimate risk ratios together with 95% CI will be undertaken. Should the regression model fail to converge, a linear model with identity link or Poisson model with logarithmic link (respectively) and robust standard errors will be employed.

\*\*\*\*\*TABLES\*\*\*\*\*  
\*\*\*\*\*

Table 1: Baseline characteristics of sleep subgroup population by treatment group

	Dexamethasone	Control
Age		
Sex		
Weight		
BMI		
ASA		
1/2		
3		
4		
Diabetes		
Chronic pain		
Opioid therapy for chronic pain		
Surgery type		
Length of surgery		
Planned use of opioids post-operatively		
PCA		
Neuraxial (intrathecal / epidural)		
Regular opioids (oral / intravenous / patch)		
PSQI score		

Sleep at home		
Sleep apnoea diagnosis		
CPAP regular use		

Table 2: Primary outcome analysis by mITT, per protocol and post-hoc adjustment for night one and secondary outcome night two.

Night	Method	Placebo	Dexamethasone	Difference (95% CI)	p-value	Missing
One (n)	mITT					
	Per protocol					
	Post-hoc adjustment					
Two (n)	mITT					

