Results will be presented as a graph for night one and in table format. A graph of the estimates from the three methods will be presented (similar to a forest plot), with the non-inferiority margin ( $\Delta$ ) of -7.5 drawn in as a line.

[figure not shown]

Image as per Schumi, J., Wittes, J.T. Through the looking glass: understanding non-inferiority. *Trials* **12**, 106 (2011). <https://doi.org/10.1186/1745-6215-12-106>

Table 3: Variables of interest post randomisation.

	Dexamethasone	Control	Estimate (95% CI)	p-value
Any nausea or vomiting up to 24 hours post-surgery				
Any antiemetic up to 24 hours post-surgery				
Worst nausea rating PACU				
Anti-emetic PACU				
Anti-emetic Day 1				
Worst nausea rating Day 1				
Any vomiting PACU				
Any vomiting Day 1				
Number of vomiting events PACU				
Number of vomiting events Day 1				
Worst pain (movement) PACU				
Worst pain (rest) PACU				
Worst pain (movement) Day 1				
Worst pain (rest) Day 1				
Sleep location night 1				
Noise level (VAS score) night 1				
Sleep location night 2				
Noise level (VAS score) night 2				
Non-study DXA during surgery				
Non-study dexamethasone PACU				
Non-study dexamethasone Day 1				

Table 4: Individual components of the Quality of Sleep Questionnaire (will not test)

	Placebo	Dexamethasone
Night one		
My sleep last night was: light (0) - deep (100)		
Last night, the first time I got to sleep I: just never could not fall		

asleep (0) - fell asleep almost immediately (100)		
Last night I was: awake all night long (0) - awake very little (100)		
Last night, when I woke up or was awakened I: couldn't get back to sleep (0) - got back to sleep immediately (100)		
I would describe my sleep last night as: a bad night's sleep (0) - a good night's sleep (100)		
I would describe the noise level last night as: very noisy (0) - very quiet (100)		
Night two		
My sleep last night was: light (0) -deep (100)		
Last night, the first time I got to sleep I: just never could not fall asleep (0) - fell asleep almost immediately (100)		
Last night I was: awake all night long (0) - awake very little (100)		
Last night, when I woke up or was awakened I: couldn't get back to sleep (0) - got back to sleep immediately (100)		
I would describe my sleep last night as: a bad night's sleep (0) - a good night's sleep (100)		
I would describe the noise level last night as: very noisy (0) - very quiet (100)		

Name \_\_\_\_\_

Date \_\_\_\_\_

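### The per-protocol exclusion window is tied to night one but is carried over to night two, so patients given non-study dexamethasone after PACU can remain in the night-two per-protocol set

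*SAP*

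**What the plan says.** Section B (Per Protocol population) contains two exposure rules. The first paragraph removes "patients who received their study drug but also receive non-study glucocorticoid within the 24 hours following surgery". The second says that the only exclusions are patients who did not get study drug and "those who got non-study dexamethasone during surgery or in PACU", and explains: "that is they received non-study dexamethasone prior to the primary outcome occurrence". The primary outcome is sleep quality on night one.

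Two other sections carry the PP analysis to night two. General principles states: "Data for all endpoints will be analysed using the modified intention-to-treat (mITT) and per protocol (PP) populations". Outcomes states: "The secondary outcome is sleep quality on night two. The same analysis will be undertaken as per night one". Neither gives night two its own PP definition.

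Non-study dexamethasone after PACU is recorded separately from intraoperative and PACU use: Table 3 has a row "Non-study dexamethasone Day 1". The Table 2 shell is titled "Primary outcome analysis by mITT, per protocol and post-hoc adjustment for night one and secondary outcome night two", but the only night-two row visible in it is mITT.

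**The concern.** The second paragraph rests on a sound principle: a PP set should be free of non-study drug received before the outcome is measured. For night two the principle is not followed, because the window stays where it was set for night one. A placebo patient given dexamethasone on the ward on Day 1 would count as per protocol for night two while already exposed to the drug under test.

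This matters because the question is one of non-inferiority. Active drug in the comparator arm can shrink a real difference and so favour the claim, and the PP analysis is the usual check on that. If the night-two PP set keeps the same exposed patients as the mITT set, agreement between the two is weaker evidence than it appears.

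**Working it through.** **Step 1: the two rules against each outcome.**

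| Rule in section B | Window closes | Non-study dexamethasone after PACU, within 24 h of surgery | Dose after 24 h, before night two |
|---|---|---|---|
| First paragraph | 24 h after surgery | excluded | retained |
| Second paragraph | end of PACU stay | retained | retained |

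Under the second paragraph, every post-PACU dose before night two is missed. Under the first, only a late gap remains. With assumed times (surgery ends at 14:00, night-two sleep starts at 22:00 the next day), the window closes at 14:00 and 22:00 − 14:00 = 8 hours are uncovered.

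The second paragraph is also narrower than its own reason. A dose given on the ward after PACU but before the first night's sleep precedes night one too, yet is not excluded.

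**Step 2: what the Day 1 field covers.** The list of postoperative variables uses the periods PACU and post-PACU up to 24 hours after incision, and Table 3 labels the corresponding nausea, vomiting and pain rows PACU and Day 1. If the dexamethasone row follows the same convention, the field stops at 24 hours after incision. Incision precedes the end of surgery, so all recorded Day 1 doses would then fall inside the first paragraph's window. The SAP does not say whether the field runs further.

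**Step 3: inputs for size.** From the Sample size section: margin 7.5 mm, SD 25.28, 195 per group, and non-inferiority judged on the two-sided 95% confidence limit. Checking that figure first, n per group = 2 × (z₁₋α + z₀.₉₀)² × SD² / margin²:

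- one-sided α 0.025 (the stated 95% interval): 2 × (1.960 + 1.282)² × 25.28² / 7.5² gives 239;
- one-sided α 0.05: 2 × (1.645 + 1.282)² × 25.28² / 7.5² gives 195.

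The stated 195 is therefore reproduced only with a 90% interval. That is a separate matter; 195 is used below simply as the planned size.

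**Step 4: dilution under assumed exposure.** Assumptions: the true night-two deficit is exactly 7.5 mm; the night-one SD applies to night two; exposure occurs only in a share c of placebo patients; and each of them takes on the full dexamethasone effect.

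- SE = 25.28 × √(2/195) = 2.56 mm
- Expected deficit = 7.5 × (1 − c)
- P(conclude non-inferiority) = Φ((7.5 − expected deficit)/SE − 1.96)

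| c | Expected deficit (mm) | (7.5 − deficit)/SE | False non-inferiority |
|---|---|---|---|
| 0% | 7.5 | 0 | 2.5% |
| 5% | 7.125 | 0.146 | 3.5% |
| 10% | 6.75 | 0.293 | 4.8% |
| 20% | 6.0 | 0.586 | 8.5% |

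**Step 5: exposure in both arms.** If a second dose adds a full further effect, the deficit is 7.5 × (1 + share exposed on dexamethasone − share exposed on placebo).

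- 10% in both arms: 7.5 × 1.00 = 7.5 mm; the rate stays at 2.5%.
- 5% placebo, 10% dexamethasone: 7.5 × 1.05 = 7.875 mm; the rate falls to about 1.8%.

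If a second dose adds nothing, exposure in the dexamethasone arm drops out and the Step 4 figures apply.

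**The case against.** Four objections deserve weight.

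*The first paragraph of section B already deals with this.* This largely stands if that paragraph governs: most, and on the reading in Step 2 all, recorded Day 1 recipients would be excluded. But the second paragraph says its exclusions are the only ones, and it is the one with a stated rationale. While both stand, an analyst may follow the second. The 24-hour window can also end before night two, although nothing in the SAP shows that doses in that gap occurred or were recorded.

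*A night-two PP analysis may not be planned.* The Table 2 shell shows only mITT for night two, and the graph of the three methods is for night one. A reader might infer that the analysis was dropped. The text does not support that firmly: General principles and Outcomes both imply it, and the table may have been cut in extraction. The uncertainty needs resolving.

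*The direction is not established.* A reader might infer that retained patients necessarily pull the arms together. The SAP gives no exposure rates by arm and nothing on the effect of a second dose, and Step 5 shows that the difference could stay the same or widen. Only the possibility of dilution is supported.

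*The effect is easily exaggerated.* It is tempting to say that non-inferiority is reached once the diluted deficit drops below 7.5 mm. The SAP judges the confidence limit. A true deficit of 9 mm with 20% placebo exposure shows as 9 × 0.8 = 7.2 mm, with a limit near 7.2 + 1.96 × 2.56 = 12.2 mm, which fails. The chance of concluding non-inferiority rises only from about 0.5% to 3.3%.

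**Conclusion.** The point holds in limited form. Followed as written, the second PP paragraph together with the General principles and Outcomes sections leaves patients in the night-two PP set whose non-study dexamethasone preceded night two. This is a stated rule applied to an outcome it was not built for. The alternative 24-hour rule narrows the gap but need not close it.

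Under placebo-only exposure of 5% to 20%, the false non-inferiority rate at the margin would be about 3.5% to 8.5% against a nominal 2.5%. These exposure rates are assumed. The calculation also uses means, whereas the SAP plans median regression on a two-peaked distribution, so it is only approximate. Exposure in both arms could remove or reverse the effect.

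The consequence is confined to a supporting analysis of the secondary outcome. The mITT analysis is principal and the night-one mITT result is untouched. The correction should be made, but the trial's main conclusion does not depend on it.

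**What to change.** 1. Reconcile the two PP definitions in section B into one rule, including whether it covers any glucocorticoid or dexamethasone only.
2. Anchor the exposure window to each endpoint: for night one, non-study drug received before night one; for night two, recorded non-study glucocorticoid received before night two, using the Day 1 field.
3. State what the Day 1 field captures and when it ends. If it stops at 24 hours after incision, say that later doses cannot be identified.
4. Confirm whether night two has a PP analysis, as the text implies. If so, show it in Table 2 with the number excluded by arm for each night.

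The cost is a short SAP edit, one derived flag and possibly one table row. The night-two PP set becomes slightly smaller and its interval slightly wider. Excluding Day 1 recipients also conditions further on a post-randomisation event: if those doses were given for nausea (an assumption), the exclusions could differ by arm and introduce selection. The tabulation of and adjustment for imbalance already planned in section B should be applied to the night-two set as well, though it cannot guarantee removal of that bias. The mITT analysis should remain principal.

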## Outcomes

The primary outcome is sleep quality on night one (as assessed using the RCSQ). As the distribution of the sleep score is not normal, median regression will be undertaken to assess the difference in medians between the two treatment groups. For the sensitivity analysis, baseline characteristics will be examined and adjustment will be made for differences between the groups. The variable, preop sleep quality, is considered a major confounder and will be included in the adjusted models.

Histogram of sleep quality night one showing two peaks.

The secondary outcome is sleep quality on night two. The same analysis will be undertaken as per night one. Some people would have been discharged on day 1 but for consistency the same variables will be adjusted for as for night one in the sensitivity analysis.

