## Sample size analysis

There are no published data available to use for accurate sample size estimation. We have collected data on 30 patients at Westmead Hospital that suit the PADDI inclusion criteria but who have not received dexamethasone. The mean RCSQ score on night one postoperatively was 50.17 mm, with a standard deviation of 25.28. A decrease in a patient's RCSQ score by 7.5mm (15% relative decrease) would be considered a clinically meaningful difference and hence we have chosen this as our non-inferiority margin (delta). To detect a non-inferiority margin of 15% with 90% probability (power), where non-inferiority is concluded if the upper endpoint of the two-sided 95% confidence interval for the difference in sleep quality is less than 7.5mm, requires a sample size of 195 patients per group (total 390 patients). Target recruitment set at 410 patients in total to account for 5% losses to follow up.

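### Sample size and margin are set on the mean scale, but the principal analysis is a difference in medians of a two-peaked score, and neither power nor margin is justified for it

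*SAP*

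**What the plan says.** - SAP, Sample size analysis: the planning figures come from a pilot ("We have collected data on 30 patients at Westmead Hospital"), summarised as a mean and an SD: "The mean RCSQ score on night one postoperatively was 50.17 mm, with a standard deviation of 25.28".
- The margin is introduced in the same section: "RCSQ score by 7.5mm (15% relative decrease) would be considered a clinically meaningful difference". It calls for 195 patients per group for 90% power, judged by a two-sided 95% confidence interval.
- SAP, Outcomes: "As the distribution of the sleep score is not normal, median regression will be undertaken to assess the difference in medians". Non-normality is the only reason given. The accompanying caption reads "Histogram of sleep quality night one showing two peaks"; the figure itself is not available to us.
- SAP, General principles: "with the mITT analysis regarded as the principal analysis". The median difference in the mITT population therefore carries the non-inferiority conclusion.
- The planned results graph sets the estimates from all three methods against a margin "of -7.5 drawn in as a line".
- No section restates power, sample size or margin for medians, and Table 2 has no row for a difference in means.

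**The concern.** A sample size based on an SD gives the power of a comparison of means. The precision of a median depends instead on how dense the scores are around the median. With two peaks, the median may lie in the trough between them, where density is low and the sample median is imprecise. The planned 90% power then says little about the analysis that will be run.

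The margin raises a related question. If dexamethasone moves some patients from good to bad sleep, the same effect can have a different size on the median and on the mean, so 7.5 mm need not mean the same on both scales.

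The reason given for medians is weak. With about 195 scores per arm, all bounded between 0 and 100, a mean difference with a robust or bootstrap interval is valid without normality. At stake is whether the only primary conclusion is informative, and against what loss of sleep quality it is drawn.

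**Working it through.** **Inputs.** From the SAP, Sample size analysis: mean 50.17, SD 25.28, margin 7.5 mm, 195 per arm, 90% power, two-sided 95% interval. A true difference of zero is assumed. Every distribution shape below is an assumption with total SD held at 25.28.

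**The plan's own figure.** n per arm = 2 × 25.28² × (z + 1.2816)² / 7.5².
- z = 1.645 (one-sided 5%): 194.6, so 195.
- z = 1.960 (the stated 95% interval): 238.8, so 239.

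So 195 is a means calculation, at a looser error rate than the stated rule. That mismatch is a separate matter, but it explains why even the means analysis falls short of 90% below. The margin is 7.5 / 50.17 = 14.9% of the pilot mean, the stated 15%.

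**Means at 195 per arm.** SE = 25.28 × √(2/195) = 2.56 mm. The 95% half-width is 1.96 × 2.56 = 5.0 mm. Power = Φ(7.5/2.56 − 1.96) = 83%.

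**Medians at 195 per arm.** SE = √(2/195) / (2f), where f is the density at the median; power = Φ(7.5/SE − 1.96). For a normal shape f = 1/(25.28 × √(2π)) = 0.01578, so SE = 0.10127/0.03156 = 3.21. The other rows are mixtures of two normals with a common within-peak SD. Each shows two peaks, and the larger share is in the higher one.

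| Assumed shape | f | SE (mm) | Half-width (mm) | Power |
|---|---|---|---|---|
| Normal | 0.01578 | 3.21 | 6.3 | 65% |
| Equal peaks, 36 mm apart | 0.01344 | 3.77 | 7.4 | 51% |
| Equal peaks, 40 mm apart | 0.01118 | 4.53 | 8.9 | 38% |
| Equal peaks, 44 mm apart | 0.00673 | 7.53 | 14.8 | 17% |
| 60:40, 40 mm apart | 0.01301 | 3.89 | 7.6 | 49% |
| 60:40, 44 mm apart | 0.01230 | 4.12 | 8.1 | 44.5% |
| 70:30, 44 mm apart | 0.01623 | 3.12 | 6.1 | 67% |
| 80:20, 50 mm apart | 0.01970 | 2.57 | 5.0 | 83% |
| 85:15, 56 mm apart | 0.02140 | 2.37 | 4.6 | 89% |
| 80:20, 54 mm apart | 0.02310 | 2.19 | 4.3 | 93% |

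Simulation of the equal-peak shapes gave SEs of 3.78, 4.46 and 6.65. The large-sample formula is therefore somewhat pessimistic at 44 mm, where 6.65 gives Φ(7.5/6.65 − 1.96) = 20%. With equal peaks 40 mm apart the half-width exceeds the margin, so an observed median difference of exactly zero would fail.

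**The margin on the two scales.**
- Uniform shift of every score: mean and median differences are equal, and 7.5 mm carries over.
- Patients move between two equal peaks: mean loss = distance between peaks × share moved. A median loss of 7.5 mm is then a mean loss of 5.6 mm (36 mm apart), 4.6 mm (40 mm) or 2.9 mm (44 mm).
- Patients move out of one dominant peak (80:20): a small shift moves the median only 0.63 mm (50 mm apart) or 0.50 mm (54 mm) per mm of mean. Solving for the share moved that lowers the median by 7.5 mm gives about 0.17 and 0.185, which are mean losses of 50 × 0.17 = 8.5 mm and 54 × 0.185 = 10.0 mm.

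**The case against.** Median regression is a valid method, specified while the data were de-identified by treatment. A mean that falls between two peaks is itself a debatable summary. The caption gives neither the heights nor the positions of the peaks, and if one peak dominates, the median can be as precise as the mean or more so. All of this stands. One qualification is that the 80:20 and 85:15 mixtures above, centred on 50.17, place about 5 to 6.5% of scores below zero, so they fit a 0-100 scale less well than the equal-peak shapes (under 2%). They still show that a loss is not inevitable.

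Three stronger readings are tempting, and the document supports none of them:
- That precision must collapse. This needs peaks of similar size with the median in the trough, which the SAP does not state.
- That the margin was agreed for means and no longer fits. The margin sentence speaks of a decrease in a patient's score, and the pilot mean serves to express it as 15%. Only the sample size is plainly a means calculation. Which way the scales diverge depends on the shape and on how treatment acts.
- That means were dropped in favour of medians after the data were seen. The SAP says that it is a second version with further analysis added, but the first version is not available.

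**Conclusion.** The mismatch holds: sample size and the 15% expression of the margin are on the mean scale, the principal test is on medians, and the SAP does not connect them. At 195 per arm and the stated interval, power is 83% for means. For medians it ranges, under assumed shapes, from about 17% to 93%, with 65% for a normal shape. The stated 90% is thus unsupported for the analysis planned and is probably not delivered, though how far it falls short cannot be known without the histogram. The 7.5 mm margin is unjustified for medians rather than shown to be wrong. It carries over under a uniform shift, is stricter in mean terms with near-equal peaks (about 4.6-5.6 mm for peaks 36-40 mm apart) and more lenient with one dominant peak. This should be fixed; confidence is moderate because the size rests on an unseen distribution.

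**What to change.** Make the difference in mean RCSQ score the principal night-one analysis: linear regression with a robust or bootstrap 95% confidence interval, judged against 7.5 mm. Use the same model for night two. Keep median regression as a labelled supportive row in Table 2, and show the histogram by arm.

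If medians stay principal, add the mean-difference row, justify 7.5 mm as a difference in medians, and restate power from the density at the median in the pooled, treatment-blinded data. Either choice should be recorded before treatment labels are joined to the scores.

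The cost is SAP wording and one further model. The downside is small: a mean summarises a two-peaked score imperfectly, and the histogram by arm lets the reader see what it hides.

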#### Quality of Sleep Questionnaire Substudy eCRF Page

##### Day 1.

Patient has diagnosed OSA?

Yes  No

Uses CPAP machine regularly?

Yes  No

Where did the patient sleep last night?

Ward  High dependency/ICU

1. My sleep last night was;

mm

2. Last night, the first time I got to sleep I:

mm

3. Last night I was:

mm

4. Last night, when I woke up or was awakened, I;

mm

5. I would describe my sleep last night as:

mm

6. I would describe the noise level last night as:

mm

7. I would describe my sleep at home as:

mm

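### The principal model omits the sleep covariate that the plan calls a major confounder, and the adjusted models leave their covariates open, so a Day 1 rating can enter

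*SAP*

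**What the plan says.** General principles reports mITT and PP analyses, "with the mITT analysis regarded as the principal analysis". Under Outcomes, "median regression will be undertaken to assess the difference in medians between the two treatment groups"; no covariate is named. Table 2 confirms the separation by giving mITT, per protocol and post-hoc adjustment their own rows for night one. Night two is to be analysed in the same way.

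Adjustment is described in three places:

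- General principles: "Further sensitivity analyses will make post-hoc adjustment for any variables exhibiting substantial imbalance across treatment arms at baseline".
- Outcomes: "For the sensitivity analysis, baseline characteristics will be examined and adjustment will be made for differences between the groups", followed by "The variable, preop sleep quality, is considered a major confounder and will be included in the adjusted models".
- Per Protocol population: "Any variables exhibiting imbalance will be adjusted for".

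Table 1, the baseline table, contains both PSQI score and Sleep at home, and also Length of surgery. The only source shown for Sleep at home is the modified RCSQ, which is about the previous night. The Day 1 eCRF page records it as "7. I would describe my sleep at home as", directly below the night-one outcome items.

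**The concern.** If a variable is expected to predict the outcome strongly and is already collected, the usual course is to name it in the principal model. Here it appears only in supportive analyses. Prognostic value is a reason to adjust; a chance difference between arms is not. A rule based on observed difference cannot be applied until the arms have been compared, and with no threshold two analysts could fit different models.

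The second matter is timing. A covariate should be settled before treatment can affect it. A rating given the morning after surgery, on the same sheet as the outcome, does not meet that condition, even though it asks about habitual sleep.

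The adjusted result is also more than a footnote. The SAP plans a graph of the three estimates against the margin of 7.5 mm, so an adjusted estimate from an unfixed model will be read next to the principal one.

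**Working it through.** **1. Is the principal model unadjusted?** The Outcomes section names treatment group only, assigns adjustment to the sensitivity analysis, and Table 2 keeps the rows apart. On this document, yes.

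**2. Which covariates enter the adjusted models?** Preoperative sleep quality enters regardless of balance, but two Table 1 variables could bear that name: PSQI score and Sleep at home. The others depend on substantial imbalance (General principles), differences between the groups (Outcomes) or any imbalance (PP). That is three wordings, with no criterion and no list.

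To see how often such a rule fires by chance, assume that imbalance means p < 0.05 and that Table 1 has 15 to 20 independent rows. The probability of at least one flag under sound randomisation is 1 − 0.95^k: 54% for k = 15 and 64% for k = 20. Rows such as weight and BMI are correlated, so this is only indicative.

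**3. When is each variable known?** The PP definition places study drug at the commencement of surgery. Sleep at home is recorded on the Day 1 page, after the drug and after night one. Length of surgery is known only when surgery ends, also after the drug. PSQI covers the past month and is listed among the baseline characteristics.

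**4. What precision is at stake under the plan's own method?** Inputs from Sample size analysis: SD 25.28 mm, 195 per group, margin 7.5 mm. The correlation r between baseline sleep and night-one RCSQ is not given, so 0.3 and 0.5 are assumed. The 195 is used here only as the group size; whether it follows from the stated decision rule is a separate matter.

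For normal scores, the large-sample standard error of a difference in medians is √(π/2) × SD × √(2/n), multiplied by √(1 − r²) after adjustment:

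- SD × √(2/195) = 25.28 × 0.1013 = 2.56 mm
- unadjusted: 1.2533 × 2.56 = 3.21 mm
- r = 0.3: 3.21 × 0.954 = 3.06 mm
- r = 0.5: 3.21 × 0.866 = 2.78 mm

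Simulated median regression (195 per arm, normal scores, no treatment effect, several batches of 500 to 1,500 runs) agrees to within simulation error:

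| | SE, mm |
|---|---|
| Unadjusted | about 3.3 |
| Adjusted, r = 0.3 | 3.1 to 3.3 |
| Adjusted, r = 0.5 | 2.8 to 2.9 |

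The SAP describes a score with two peaks. In two assumed two-peaked scenarios the standard error fell from 4.4 to 3.8 mm and from 4.7 to 3.6 mm. Those shapes are assumptions, and some quantile fits reached their iteration limit, so only the direction should be relied on.

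**5. How far could chance imbalance move the unadjusted estimate?** With normal scores, a baseline difference of two standard errors shifts it by 2 × r × SD × √(2/n):

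- r = 0.3: 2 × 0.3 × 2.56 = 1.5 mm
- r = 0.5: 2 × 0.5 × 2.56 = 2.6 mm

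Both are to be set against the 7.5 mm margin.

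**The case against.** An unadjusted principal analysis of a randomised trial is valid, and many plans choose one. That stands. The word confounder might lead a reader to infer that the principal result is biased. The documents do not support this: allocation is randomised, so the cost is precision and exposure to chance imbalance.

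The plan fixes preoperative sleep quality in advance for the adjusted models, so it would be wrong to say that all covariates are chosen by imbalance. It would also be wrong to call the mITT sensitivity analysis the only adjusted one, since the PP section provides for adjustment too. In PP the case for adjusting is stronger, because exclusions after randomisation can unbalance the arms, but that makes the missing rule matter more.

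The SAP says that the mITT analysis follows the main PADDI plan, which is not shown and might name covariates. The Outcomes section and Table 2 of this SAP nevertheless present the mITT comparison as distinct from adjustment.

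A reader might infer that adjusting for Sleep at home favours non-inferiority. The documents give no basis for a direction. A bad night could lower the home rating, or raise it by contrast, or leave it unchanged, because the item asks about sleep at home and not about last night.

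Finally, adding PSQI to a median regression changes the target from the difference in group medians to a difference conditional on PSQI. With a two-peaked score the two can differ. This is a real cost. This SAP version was also written with data in hand and describes the outcome histogram, so any change to the principal model must be made without reference to treatment.

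**Conclusion.** The point holds as a recommended improvement, not as a fault that invalidates the trial. Three things are plain in the SAP: the principal model omits a variable that the plan itself calls major; the remaining covariates in the mITT sensitivity and PP analyses have no selection criterion; and a Day 1 rating is labelled baseline and can enter the adjusted models, either through the imbalance rule or as the undefined preoperative sleep measure.

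Under normal scores the gain from adjustment is slight at r = 0.3 and clear at r = 0.5. It may be larger with two peaks. It rests on a correlation that the documents do not give. Power gains calculated for a difference in means should not be quoted, because the plan does not use that test. The possible distortion from Sleep at home cannot be sized or signed from the documents.

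**What to change.** Before treatment codes are linked to the data:

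1. Define preoperative sleep quality as the baseline global PSQI, continuous, and include it in the principal median regression for both nights.
2. Replace selection by imbalance, in mITT and PP alike, with one short list of covariates fixed in advance, chosen for prognostic value and settled before study drug. Age, sex, chronic opioid therapy and surgery type are candidates from Table 1. Sleep apnoea diagnosis is asked on the Day 1 page; it can qualify as pre-existing history if the SAP says so.
3. Remove Sleep at home and Length of surgery from the adjustment set, and report Sleep at home as a Day 1 item.
4. Keep the unadjusted difference in medians as a supportive row in Table 2 and in the graph.
5. State that the principal estimate is conditional on PSQI, and give a simple imputation rule for any missing PSQI values.

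No new data are needed. The cost is SAP wording, the change of estimand in item 5, and a dated statement that the change was made blind to treatment.
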